### 3.1.3 Follow-up Phase

Follow-up will start once the Intervention Phase is finished and will continue until hospital discharge or 90 days post-randomization, whichever comes first.

## 3.2 Allocation to Treatment Groups and Blinding

**Randomization and Monitoring:** Randomization will be performed in 1:1 permuted blocks using a randomization module available in Research Electronic Data Capture (REDCap). Treatment allocation will be concealed to the clinical team until after enrollment has been confirmed. Compliance with assigned treatment group, adherence to ventilator protocol, and adherence to protocolized co-interventions will be monitored.

**Blinding:** The intervention will not be blinded to clinicians or investigators. Blinding is not feasible for an intervention as fundamental and as clinically labile as ventilator management. To minimize selection bias that could occur due to pre-enrollment awareness of  $\Delta P$  assignment, randomization will occur only after informed consent has been obtained.

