## PROTOCOL SYNOPSIS

Study Title	Pediatric Acute Respiratory Distress Syndrome (ARDS) Management (PARMA) Trial
Funder	NICHD
Clinical Phase	Phase 2A
Study Rationale	
Acute respiratory distress syndrome (ARDS) is characterized by acute onset of diffuse, bilateral pulmonary edema and severe hypoxemia not fully explained by cardiac failure, representing 10% of mechanically ventilated children in pediatric intensive care units (PICUs), with an associated mortality rate of up to 20%. Lung-protective ventilation with lower tidal volumes and driving pressures (defined as plateau pressure minus positive end-expiratory pressure, <math>\Delta P</math>) is the backbone of ventilation strategies in adults, with variable adoption in pediatrics. However, pre-clinical and observational clinical data suggest that the tidal volume and <math>\Delta P</math> limits extrapolated from adults are too restrictive for children. As lower tidal volumes and <math>\Delta P</math> are associated with worse oxygenation and ventilation, overly restrictive lung-protective ventilation may contribute to prolonged ventilation via worse gas exchange in pediatrics with no improvement in outcomes, thus justifying an explicit trial of different <math>\Delta P</math> strategies in pediatric ARDS.

Study Objective(s)	
Primary
 
 
• To test the efficacy of a high <math>\Delta P</math> (25 cmH2O) versus low <math>\Delta P</math> (15 cmH2O) ventilation on time to resolution of ARDS (alive and PaO2/FIO2 > 300), hypothesizing faster hypoxemia resolution (Aim 1) with high <math>\Delta P</math>
 
 
Secondary
 
 
• To test the efficacy of a high <math>\Delta P</math> (25 cmH2O) versus low <math>\Delta P</math> (15 cmH2O) ventilation on lung aeration , hypothesizing improved lung aeration (Aim 2) with high <math>\Delta P</math>
 

Test Article(s) (If Applicable)	High $\Delta P$ (25 cmH 2 O) versus low $\Delta P$ (15 cmH 2 O) mechanical ventilation strategy
Study Design	Parallel group, unblinded, randomized controlled trial
Subject Population	Inclusion Criteria

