Ancillary therapy documentation	Required	While the order of use, or the decision to use, the above therapies are not mandated, all ancillary therapy use will be recorded daily
Ventilator weaning (may occur after Intervention Phase)	CHOP Ventilator Weaning Pathway	The CHOP PICU ventilator weaning pathway is initiated when there is spontaneous breathing, PEEP $<$ 12 cmH 2 O and FIO 2 $<$ 0.50; the pathway reduces respiratory rate, PEEP, and pressure support every 4 hours as tolerated until extubation readiness test
Extubation readiness (may occur after Intervention Phase)	CHOP ERT pathway (embedded in Ventilator-Weaning Pathway)	A spontaneous breathing trial (PEEP $\leq$ 8 cmH 2 O and pressure support $\leq$ 8 cmH 2 O for 1 to 2 hours) is initiated when PEEP $\leq$ 8 cmH 2 O and FIO 2 $\leq$ 0.40; an endotracheal tube leak is assessed and dexamethasone recommended for leak $>$ 20 cmH 2 O; subjects who pass this trial are extubated within 6 hours

**Electrical Impedance Tomography (EIT):** EIT is an FDA-approved non-radiating method of imaging lung aeration currently used at CHOP for clinical care, with an associated existing EPIC order. For PARMA, EIT will be performed post-randomization after stabilization of settings on the assigned  $\Delta P$  study arm and no later than 8 hours after initiation of assigned protocol. EIT measurements will be repeated 24 to 72 hours after initial post-randomization EIT measurements while on the assigned ventilator protocol. If the subject is off of the assigned protocol (i.e., failure criteria or early termination), the repeat EIT will be deferred. EIT images will not routinely be made available to the clinical team, as they require some significant offline processing.

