For Aim 2, pre- and post-randomization EIT images (in the immediate 8 hours after randomization) will be used to determine the change in aeration. Lung images will be divided into 4 ROIs along the axial and sagittal planes, and impedance (i.e., aeration) will be determined for each region. Post-randomization end-expiratory lung impedance (EELZ) values and elastance (measured at the ventilator) will be compared to pre-randomization to determine whether ventilator changes results in recruitment (increased EELZ; unchanged or improved elastance), overdistension (increased EELZ; worsened elastance), or atelectasis (decreased EELZ; worsened or unchanged elastance). This analysis will be repeated with the second set of post-randomization EIT measurements (performed 24 to 72 hours after randomization), again compared to pre-randomization EIT. We will compare the proportion of subjects with improved recruitment and with overdistension, relative to pre-randomization EIT, between high and low  $\Delta P$  arms, with effect sizes presented as relative risk (RR). RR > 1 implies a greater proportion of subjects with the reported aeration (e.g., recruitment) with high  $\Delta P$ .

We will compute the posterior probability under minimally informative priors for any benefit when comparing 28-day mortality, PICU mortality, and hospital mortality between high and low  $\Delta P$  arms. Effect sizes will be presented as RR, with RR < 1 meaning lower mortality risk with high  $\Delta P$ . Additional analyses will be conducted with standardized priors reflecting pessimistic (priors centered at RR 1.2) and optimistic (priors centered at RR 0.8) scenarios, and with data-driven priors using effect sizes from prior adult  $V_T$  trials, including ARMA.

Analyses of VFDs and other free-day clinical endpoints will be conducted as described above for hypoxemia resolution, with death prior to the main event being treated as a competing risk and effect sizes presented on the HR scale with HR > 1 meaning superiority of high  $\Delta P$  ventilation. The main analyses will be conducted using minimally informative priors (as per main analysis), with additional analyses conducted using standardized priors reflecting pessimistic (priors centered at HR 0.8) and optimistic (priors centered at HR 1.2) scenarios, and with data-driven priors using effect sizes from prior adult  $V_T$  trials.

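### The reason for not blinding covers ventilator delivery only, and the protocol provides no arm-masked processing of the offline EIT data behind Aim 2, although the EELZ step could be masked

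*Protocol*

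**What the plan says.** Section 3.2 of the protocol, under Blinding, says: "The intervention will not be blinded to clinicians or investigators". Its justification follows: "Blinding is not feasible for an intervention as fundamental and as clinically labile as ventilator management". Section 9.1.2 repeats both statements, and the Retention paragraph of Section 9.5 gives a similar reason.

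On EIT, Section 3.1.2 says: "EIT images will not routinely be made available to the clinical team, as they require some significant offline processing".

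Section 6.3.2 describes the Aim 2 analysis. On the images: "Lung images will be divided into 4 ROIs along the axial and sagittal planes, and impedance (i.e., aeration) will be determined for each region". On the second component: "elastance (measured at the ventilator) will be compared to pre-randomization". Each child is then classified by direction of change. Two of the three labels are "recruitment (increased EELZ; unchanged or improved elastance") and "overdistension (increased EELZ; worsened elastance"); the third, atelectasis, requires decreased EELZ with worsened or unchanged elastance. No numeric cut-off is given. The proportions with recruitment and with overdistension are compared between arms as relative risks.

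The Synopsis states the expected direction: "hypothesizing improved lung aeration (Aim 2) with high" ΔP. Section 9.2 says that data reaching the data coordinating center carry a subject ID, but does not describe this as hiding the arm.

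**The concern.** The justification for not blinding fits the bedside. Staff who set and monitor the ventilator cannot be kept unaware of ΔP. It does not fit the derivation of EELZ, which is done offline and whose images are not routinely returned to the clinical team. Masking that step would not interfere with care.

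Aim 2 is the mechanistic part of the trial. Section 9.4.4 says the trial intends to identify a plausible mechanism for benefit from high ΔP and to inform a larger multicenter trial. Because each label turns on the sign of a change, a small EELZ difference around zero decides the category. An analyst who knows the arm and the hypothesis could, without intending to, choose a recording segment, reject an artefact or handle baseline drift in a way that differs between arms. That would be detection bias. It can largely be prevented beforehand, but masking cannot be restored once the files have been processed with the arm known.

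**Working it through.** **Step 1. Which steps does the stated reason for not blinding cover?**

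| Step | Where described | Covered by the stated reason? | Can it be masked? |
|---|---|---|---|
| Setting and monitoring the ventilator | 3.1.2, 3.2 | Yes | No |
| Deriving EELZ from EIT recordings | 3.1.2, 6.3.2 | No, it is offline | Largely, with coded files |
| Elastance | 6.3.2 | Measured at the ventilator | No, not at source |
| Combining both into a label | 6.3.2 | No | Yes, if done by program |

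Elastance cannot be masked at source because Section 6.3.2 defines it for Aim 1B as ΔP divided by tidal volume, and ΔP is the assigned treatment.

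**Step 2. In which direction would arm-aware EELZ choices act?** Suppose choices turn a small decrease in EELZ into an increase. Under the Section 6.3.2 definitions:

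- elastance unchanged: atelectasis becomes recruitment;
- elastance improved: a child with no listed label becomes recruitment;
- elastance worsened: atelectasis becomes overdistension.

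The same choice can therefore add to the favourable or the unfavourable label. The net direction depends on the elastance changes and cannot be derived from the protocol.

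**Step 3. How large could the effect on the recruitment comparison be?** The protocol gives no figure for recruitment frequency or reader effect, so there is no stated figure to reproduce. All inputs here are assumptions: the same true recruitment proportion p in both arms, with a shift s upward in the high arm and downward in the low arm.

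RR = (p + s) / (p − s)

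| p | s = 3 points | s = 5 points |
|---|---|---|
| 25% | 28/22 = 1.27 | 30/20 = 1.50 |
| 50% | 53/47 = 1.13 | 55/45 = 1.22 |

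A low base rate enlarges the ratio, so both rows are needed.

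**Step 4. A milder case, with a shift in one arm only.** Assume a share f of non-recruited children in the high arm is read as recruited. Then pH = p + f(1 − p) and pL = p. Take 80 children per arm (160 / 2, assuming all contribute EIT data). Borrow the primary outcome's criterion of more than 90% posterior probability of benefit; the protocol sets no such criterion for Aim 2. With a flat prior and a normal approximation:

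chance of meeting the criterion = Φ[(pH − pL)/SE − 1.28], with SE = √[pH(1 − pH)/80 + pL(1 − pL)/80]

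Example with p = 0.30 and f = 0.10: pH = 0.37, SE = 0.0744, and Φ(0.94 − 1.28) = 0.37. For p between 30% and 50%:

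| f | RR | Chance of meeting the criterion with no true effect |
|---|---|---|
| 0 | 1.00 | 10% |
| 5% | 1.05 to 1.12 | 17% to 21% |
| 10% | 1.10 to 1.23 | 26% to 37% |

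These figures show sensitivity only. They do not estimate what would happen in this trial.

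**The case against.** A reader might infer from Section 3.2 that EIT recordings will be read with arm and hypothesis known. The document does not say that. The sentence concerns blinding of the intervention, and no section names who processes the EIT files or what that person sees. Section 4.2.1 lists an imaging protocol, Section 9.2 plans a manual of operations, and a statistical analysis plan may exist; any of these could specify masking. This stands: the point is that the protocol discusses blinding in two dedicated sections, gives a reason limited to ventilator delivery, and makes no provision for the offline step.

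Scope for judgement is also limited. The split into four regions reads as geometric, EELZ is numeric, and EIT processing cannot alter the ventilator elastance. Segment selection, artefact rejection and drift handling are not mentioned in Section 6.3.2, so their influence is assumed. This stands too, and the effect may be small.

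A reader might further infer that any bias must favour high ΔP. Step 2 of the working shows why that does not follow: raising EELZ can also produce overdistension.

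Finally, it would be wrong to restrict the no-blinding statement to bedside staff. Under Section 3.1.2 the research team reviews ventilator settings and compliance at least twice a day, and under Section 4.3 the principal investigator records the primary reason for withdrawal after failure. Investigators are unblinded, and the statement is true as it stands.

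**Conclusion.** The point holds as a gap in the protection of a secondary aim. The reason for not blinding does not reach the offline EIT processing, no arm-masked processing is provided, and the direction-only labels leave the comparisons open to small arm-dependent choices. The primary outcome, sample size and power are untouched.

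The size and net direction of any bias are unknown. Under assumed opposite shifts of 3 to 5 points and no true effect, the recruitment RR would be 1.27 to 1.50 at a 25% base rate and 1.13 to 1.22 at 50%; one-sided shifts give smaller ratios. These ranges rest on assumed base rates and assumed shifts, and on the premise that the analyst knows the arm, which the protocol neither states nor excludes. The change is worth making because it is inexpensive and useful only before the recordings are processed.

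**What to change.** Keep the statement in Sections 3.2 and 9.1.2 that clinicians and investigators are unblinded to the intervention. Add there and in Section 6.3.2 that:

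1. EIT recordings are exported under a random code that hides arm, visit and ventilator pressure data;
2. the existing analyst performs segment selection, artefact handling, region division and EELZ derivation on the coded files;
3. the EELZ values are locked before the code is broken;
4. ventilator elastance and arm are merged only afterwards, and labels are assigned by program using rules set in advance.

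The cost is a file-coding step and a few sentences. It needs no new procedure or visit and does not affect care. No extra reader is needed provided the analyst is not on the team that monitors ventilator settings; the protocol does not say who the analyst is, so this should be confirmed. The downside is that masking is partial: the amplitude of tidal impedance may hint at the arm, and elastance cannot be masked at source.

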## 3.3 Study Duration, Enrollment and Number of Sites

### 3.3.1 Duration of Subject Study Participation

The study duration per subject will begin at screening, and for enrolled subjects, will last up to hospital discharge or 90 days after randomization, whichever comes first.

### 3.3.2 Total Number of Study Sites/Total Number of Subjects Projected

The study will be conducted entirely at CHOP, with screening in the PICU and follow-up until hospital discharge or within 90 days of randomization.

We will enroll (consent) 180 subjects to produce an anticipated 160 evaluable subjects.

## 3.4 Study Population

Eligibility criteria were designed to enroll children with Berlin-defined ARDS without limitations of care and expected to survive > 72 hours in the CHOP PICU. We specifically chose Berlin criteria rather than the 2015 or 2022 PALICC pediatric ARDS criteria for two reasons. First, the PALICC defines ARDS severity using oxygenation index, rather than  $\text{PaO}_2/\text{FIO}_2$ , which incorporates mean airway pressures (mPaw). However, the high  $\Delta P$  arm in PARMA will have higher mPaw (by definition), and the Berlin definition (using  $\text{PaO}_2/\text{FIO}_2$ ) may be a more reliable metric of hypoxemia severity and resolution. Second, PALICC has less restrictive radiographic criteria (unilateral opacities allowed), and so we anticipate all subjects with Berlin ARDS in PARMA would also meet criteria for the PALICC definition of pediatric ARDS.

### **3.4.1 Inclusion Criteria (examples)**

- 1) age > 2 weeks (> 38 weeks corrected gestational age) and < 18 years (not yet had 18th birthday)
- 2) acute ( $\leq$  7 days of inciting etiology) respiratory failure requiring invasive mechanical ventilation
- 3) ventilated with endotracheal tube or tracheostomy for  $\leq$  7 days from inciting etiology (e.g., pneumonia, sepsis, trauma, aspiration, cardiac arrest, pancreatitis, engineered T cell therapy, among others) onset
- 4) hypoxemia defined as  $\text{PaO}_2/\text{FIO}_2 \leq 300$  (or  $\text{SpO}_2/\text{FIO}_2 \leq 315$ ) on  $\text{PEEP} \geq 5 \text{ cmH}_2\text{O}$  on two consecutive measurements 4 hours apart and sustained at the time of consent and randomization
- 5) bilateral opacities on chest radiograph as determined by radiologist, clinical attending, or PI

### **3.4.2 Exclusion Criteria**

- 1) hypoxemia caused primarily by hydrostatic pulmonary edema from heart failure or fluid overload
- 2) non-palliated or unrepaired cyanotic congenital heart disease
- 3) ventilated via tracheostomy at baseline prior to acute illness
- 4) obstructive airway disease determined to be the primary cause of respiratory failure
- 5) severe moribund state not expected to survive  $> 72$  hours
- 6) any limitations of care at time of screening
- 7) escalation to high frequency oscillatory ventilation or extracorporeal support (i.e., meeting PARMA protocol failure criteria) at time of screening
- 8) previous enrollment in this study

## 4 STUDY PROCEDURES

### 4.1 Screening Visit

All PICU patients will be screened twice daily (once on weekends) by trained study staff. Eligible patients will be approached  $\leq$  24 hours of meeting criteria, defined as time of second confirmatory hypoxemia measurement.

### 4.2 Study Treatment Phase

#### 4.2.1 Visit 1

Subjects will have EIT (Timpel) bands placed and measurements taken at pre-randomization ventilator settings within 4 hours of consent. Randomized  $\Delta P$  treatment arm will be delivered by PCV, with peak pressures set according to  $\Delta P$  arm and PEEP assigned according to a PEEP/FIO2 grid. Specific ventilator management details are provided below.

- Ventilator protocol
- Imaging protocol
- Co-intervention protocol
- Medical Record Review for data collection

#### 4.2.2 Visit 2

EIT measurements will be repeated 24 to 72 hours after initial post-randomization EIT measurements while on the assigned ventilator protocol. If the subject is off of the assigned protocol (i.e., failure criteria or early termination), the repeat EIT will be deferred.

### 4.3 Subject Completion/Withdrawal

Successful Completion: Achievement of the primary outcome terminates the assigned ventilator protocol. After 28 days (timing of primary outcome), providers are encouraged but not mandated to continue with the assigned protocol. We will continue to gather data until hospital discharge up to 90 days after randomization.

Failure Criteria: Refractory hypoxemia or respiratory acidosis will typically prompt escalation to high frequency oscillatory ventilation or extracorporeal support, and will trigger a suspension of the assigned  $\Delta P$  protocol. In some cases, the clinical team may wish to cross over into pressures used in the alternative  $\Delta P$  protocol, which will still count as failure criteria. Subsequent ventilator management, including when weaning off of conventional or high frequency oscillatory ventilation or extracorporeal support, will be left to a physician's discretion. The CHOP PI ([name]) will record the primary reason for withdrawal. Every attempt will be made to continue data collection, providing that the family/patient concurs with continued data collection.

Early Termination: The assigned ventilator protocol can be suspended or permanently discontinued if, in the treating physician's judgment, it is no longer safe to continue. A protocol deviation will be documented only if the subject is withdrawn from the study due to a lack of protocol adherence absent clinical indication. Parents and legal guardians can also request withdrawal from the study and discontinue study procedures. Every attempt will be made to continue data collection, providing that the family/patient concurs with continued data collection.

#### **4.4 Stopping Rules**

The DSMB will review all trial data, with a focus on safety data, at a frequency of no less than every 6 months (approximately every 20 enrolled subjects). While we do not provide explicit stopping rules for PARMA, the DSMB can make recommendations to change/alter the trial procedures or to stop the trial for safety based on their review of adverse events.

## 5 STUDY EVALUATIONS AND MEASUREMENTS

### 5.1 Screening and Monitoring Evaluations and Measurements

#### 5.1.1 Medical Record Review

Detailed clinical data will be recorded, including demographics (age and sex), severity of illness (Pediatric Risk of Mortality [PRISM] IV; Pediatric Logistic Organ Dysfunction [PELOD] 2), co-morbidities (prematurity, immunocompromised status, stem cell transplant), and ARDS etiology (e.g., pneumonia, sepsis, trauma, aspiration). Pre- and post-randomization ventilator settings, oxygenation, ancillary therapy use, and adverse events will be documented daily until discontinuation of invasive ventilator support. Organ failures (PELOD 2 score derived from labs), vasopressor support, and clinical outcomes will be monitored until hospital discharge. REDCap will serve as the data collection interface.

